7.1.3 Formulation, Packaging, and Labeling

Clindamycin phosphate, USP (IV) is supplied in vials with clindamycin 150 mg/mL and must be diluted prior to IV administration.

Clindamycin hydrochloride, USP (PO capsules) is available as 150 mg and 300 mg capsules.

Clindamycin palmitate hydrochloride, USP for oral solution is available in 100 mL bottles for reconstitution.

Each formulation is approved for use in the United States.

7.1.4 Product Storage and Stability

Clindamycin phosphate (IV), clindamycin hydrochloride (PO capsules), and clindamycin palmitate (PO oral solution) will all be stored at room temperature (20–25^o C). Diluted clindamycin phosphate (IV) is stable at room temperature for at least 16 days and refrigerated for at least 32 days. Reconstituted clindamycin palmitate hydrochloride, USP for oral solution is stable for 2 weeks at room temperature and should not be refrigerated. See the MOP for detailed information.

7.2 Preparation and Administration of Study Intervention/Study Drug

Clindamycin phosphate, USP (IV) is supplied in vials with clindamycin 150 mg/mL and must be diluted prior to IV administration. The concentration of clindamycin in diluent for infusion should not exceed 18 mg/mL. The drug will be infused over 30 (+/- 5) minutes. Infusion rates should not exceed 30 mg/minute. The pharmacy will prepare the IV formulation, and the dose administered will be based on TBW.

Clindamycin hydrochloride, USP (PO capsules) is available as 150 mg and 300 mg capsules, and the dose will be dispensed based on TBW (see **Appendix III** for dosing).

Clindamycin palmitate hydrochloride, USP for oral solution is available in 100 mL bottles and will be prepared in the pharmacy at each site based on the reconstitution recommendation in the label. The dose administered will be based on TBW.

Refer to the MOP for additional details regarding drug procurement, drug preparation, and administration.

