2.3 Potential Risks and Benefits

2.3.1 Potential Risks

Risks of Blood Draws

There are small risks to blood sampling, usually some pain/discomfort with the blood stick. Every effort will be made to avoid additional (to standard of care) sticks for this study by timing clinical blood draws to coincide with timed samples when possible and the use of existing IV lines when feasible for the blood draws.

Risks of Clindamycin

From the FDA label and review of the literature, the following are adverse reactions of clindamycin: antibiotic-associated colitis, pseudomembranous colitis, abdominal pain, nausea, and vomiting; hypersensitivity reactions (maculopapular rash and urticaria have been observed during drug therapy; generalized mild-to-moderate morbilliform-like skin rashes are the most frequently reported of all adverse reactions; rare instances of erythema multiforme, some resembling Stevens-Johnson syndrome, have been associated with clindamycin; a few cases of anaphylactoid reactions have been reported). Organ systems that are affected include skin and mucous membranes (pruritus, vaginitis, and rare instances of exfoliative dermatitis have been reported); liver (jaundice and abnormalities in liver function tests have been observed during clindamycin therapy); renal system (although no direct relationship of clindamycin to renal damage has been established, renal dysfunction as evidenced by azotemia, oliguria, and/or proteinuria has been observed in rare instances); hematopoietic (transient neutropenia [leukopenia] and eosinophilia have been reported; reports of agranulocytosis and thrombocytopenia have been made; no direct etiologic relationship to concurrent clindamycin therapy could be made in any of these instances); local reactions (pain, induration, and sterile abscess have been reported after IM injection and thrombophlebitis after IV infusion); musculoskeletal (rare instances of polyarthritis have been reported); cardiovascular (rare instances of cardiopulmonary arrest and hypotension have been reported following too rapid IV administration). There is minimal additional risk to the participants who are receiving clindamycin as part of their routine medical care.

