7 STUDY PRODUCT DESCRIPTION

7.1 Dosage and Study Drug Information

7.1.1 Rationale for Dose Selection

A dose of 30–40 mg/kg/day divided q6h or q8h with a maximum dose of 2.7 g/day is selected based on current labeling. Patients who are receiving clindamycin as part of their routine care are also eligible to participate if their dose can be adjusted to be at least 30 mg/kg/day upon enrollment. The dose administered will be based on TBW. Because bioavailability is estimated at 85%, the same dose will be used for oral administration as is used for IV dosing. Both solution and capsule preparations will be included in this study because both oral formulations are used in clinical practice, and it will allow the inclusion of those patients who cannot swallow pills. In the absence of PK data, we assume that drug clearance will be comparable in obese pediatric patients compared to non-obese pediatric patients. Therefore, a dosing regimen 30–40 mg/kg per day and a maximum dose of 2.7 g/day should provide exposures similar to those used in children and adolescents with a normal BMI. It is predicted to be safe in the obese population because similar doses are currently used per routine care.

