7.1.2 Dose and Timing

Both q6h and q8h dosing will be allowed for both oral and IV dosing of clindamycin. For children receiving clindamycin as part of clinical care, this protocol will not prescribe a route of administration or dosing interval; the dose, route of administration, and dosing interval prescribed by the treating physician will be recorded on the CRF. However, if the prescribed dose is less than the lowest dose for this study, the dose of clindamycin will be changed to comply with the study dose. Dosing greater than 2.7 g/day will be allowed for children receiving clindamycin as part of clinical care. See **Section 5.2.1** for duration of therapy.

IV dosing: A minimum of 2 study doses of IV clindamycin will be administered. The dose administered will be based on TBW at 30–40 mg/kg/day divided q6h or q8h with a maximum dose of 2.7 grams/day. The drug will be administered over 30 (+/- 5) minutes. The venous access line will be flushed per local practice after completion of IV administration, and the time of the end of flush will be documented. It is preferred that the flush be ≤ 1 minute after the end of infusion.

Oral dosing: For those participants who are receiving clindamycin as a solution, they will receive 30–40 mg/kg/day divided q6h or q8h. For those participants receiving the capsule formulation, they will receive the dose of clindamycin defined in **Appendix III**. Only whole capsules will be used. The oral solution will be used for those participants who cannot swallow capsules. No more than 12 PO study drug doses will be administered as part of this study.

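### The uniform 25–35 minute infusion window is not reconciled with the 30 mg/minute ceiling: its short end exceeds the ceiling for q8h doses above 750 mg, and no permitted time complies above 1050 mg

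*Supplement*

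**What the plan says.** Section 7.2 (Preparation and Administration) gives the window and the ceiling in consecutive sentences: "The drug will be infused over 30 (+/- 5) minutes. Infusion rates should not exceed 30 mg/minute". Section 7.1.2 (Dose and Timing) repeats the window: "The drug will be administered over 30 (+/- 5) minutes". Neither section makes the time depend on the dose.

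Section 7.1.2 sets IV dosing at 30–40 mg/kg/day on total body weight, "divided q6h or q8h with a maximum dose of 2.7 grams/day". It then opens an exception: "Dosing greater than 2.7 g/day will be allowed for children receiving clindamycin as part of clinical care". No upper limit is attached to that exception, and the dosing interval for these children is left to the treating physician. Section 7.1.1 adds that children on routine-care clindamycin "are also eligible to participate if their dose can be adjusted to be at least 30 mg/kg/day upon enrollment".

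Among the known risks, section 2.3.1 records that "rare instances of cardiopulmonary arrest and hypotension have been reported following too rapid IV administration".

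**The concern.** A reader at the bedside sees a tolerance of five minutes either way and may treat all of it as available. For the larger doses it is not: part of the window gives a rate above the limit set in the very next sentence. For the largest doses that the exception allows, none of the window complies, and staff would have to depart from one instruction or the other.

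The probable origin is visible in the supplement. Earlier protocol versions specified a flat 30 minutes, at which the capped q8h dose runs at exactly the ceiling. The tolerance was added later, and the ceiling was left as it was.

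What is at stake is safety consistency and avoidable protocol deviations. Section 16.6 counts any noncompliance with the protocol as a deviation. The doses concerned are not exotic for this population: enrolment favours children above the 97th BMI percentile (section 5), and one of the two age groups is 12 to under 18 years.

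**Working it through.** **Inputs.** Infusion time 25, 30 or 35 minutes (7.1.2, 7.2). Ceiling 30 mg/min (7.2). Cap 2.7 g/day, given q6h or q8h (7.1.2). Dose 30–40 mg/kg/day on total body weight (7.1.2).

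**Formulas.** Rate = (daily dose ÷ doses per day) ÷ infusion minutes. Largest compliant dose = 30 mg/min × infusion minutes.

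**Step 1: the nominal case.** 2700 mg ÷ 3 = 900 mg, and 900 ÷ 30 = 30.0 mg/min. The capped q8h dose over the nominal time equals the stated ceiling exactly and leaves no margin.

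**Step 2: capped doses across the window.**

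| Dose | 25 min | 30 min | 35 min |
|---|---|---|---|
| q8h at cap: 2700 ÷ 3 = 900 mg | 36.0 | 30.0 | 25.7 |
| q6h at cap: 2700 ÷ 4 = 675 mg | 27.0 | 22.5 | 19.3 |

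(mg/min.) At 25 minutes the q8h dose is 36.0 ÷ 30 = 1.20, or 20% over the ceiling. The q6h dose complies throughout.

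**Step 3: largest dose that meets the ceiling.**

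| Infusion time | Largest dose | As daily dose, q8h | As daily dose, q6h |
|---|---|---|---|
| 25 min | 30 × 25 = 750 mg | 2.25 g | 3.0 g |
| 30 min | 30 × 30 = 900 mg | 2.7 g | 3.6 g |
| 35 min | 30 × 35 = 1050 mg | 3.15 g | 4.2 g |

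Within the 2.7 g/day cap, therefore, only q8h doses above 750 mg are affected, and only at the short end of the window. On q6h a dose above 750 mg already needs more than 3.0 g/day, so it falls under the exception.

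**Step 4: weights at which 750 mg q8h is passed.** 750 × 3 = 2250 mg/day. At 40 mg/kg/day: 2250 ÷ 40 = 56.25 kg. At 30 mg/kg/day: 2250 ÷ 30 = 75 kg. At exactly 750 mg the ceiling is met at 25 minutes; only larger doses exceed it.

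**Step 5: where no time in the window complies.** This needs more than 1050 mg per dose. If the cap is not applied, the weight thresholds are:

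- q8h: 3150 ÷ 30 = 105 kg, or 3150 ÷ 40 = 78.75 kg
- q6h: 4200 ÷ 30 = 140 kg, or 4200 ÷ 40 = 105 kg

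Illustration, with weight and regimen assumed: 110 kg at 30 mg/kg/day on q8h is 3300 ÷ 3 = 1100 mg, which runs at 44.0, 36.7 and 31.4 mg/min over 25, 30 and 35 minutes. A dose between 900 and 1050 mg can still comply toward the long end: 1000 mg over 35 minutes is 28.6 mg/min.

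**The case against.** The best reply is that the two sentences are cumulative limits. A site giving 900 mg over 25 minutes breaks an explicit instruction printed beside the window, so it is not following the protocol. For any dose up to 1050 mg some permitted time satisfies both. This stands. A reader might infer that the two rules can never be met together; the documents do not support that for any dose within the cap. There the fault is a window too wide at its short end, with no stated precedence.

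It is also fair that the outright conflict is narrow. It arises only for children already on clindamycin as clinical care whose dose exceeds the cap far enough. A reader might infer from the 30 mg/kg/day floor in section 7.1.1 that every routine-care child above 105 kg on q8h must receive more than 1050 mg. The text does not settle whether the cap limits that floor, and it gives no expected weights or doses.

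A further temptation is to tie the events listed in section 2.3.1 to 36 mg/min. That section gives no rate, so the link cannot be drawn from the documents. Section 2.3.1 shows only why a rate ceiling matters.

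Finally, section 7.2 refers to the MOP for details of administration. The MOP is not shown and may contain dose-specific times. If so, the practical risk is smaller, but the protocol text would still disagree with itself.

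**Conclusion.** The point holds in limited form. The window is stated without regard to dose, and for q8h doses above 750 mg it includes times that exceed the protocol's own ceiling, by up to 20% at the capped dose. Capped q6h dosing is clear of the problem. Outright incompatibility is confined to single doses above 1050 mg, which the exception permits because it has no stated upper limit.

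The rates and dose thresholds follow directly from figures in the protocol and need no assumption. The weight thresholds assume dosing at exactly 30 or 40 mg/kg/day, and those in step 5 also assume that the cap does not apply. How many participants would be affected cannot be estimated from the documents.

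No PK estimate or conclusion changes, because section 6.3 already requires the actual start, stop and flush times to be recorded. Severity is moderate: a safety-consistency repair that does not bear on the validity of the analysis.

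**What to change.** Reconcile the infusion-time window, the rate ceiling and the permitted doses in sections 7.1.2 and 7.2, so that every dose the protocol allows, including those under the routine-care exception, can satisfy both limits. State which limit governs where they disagree: above 750 mg at 25 minutes, above 900 mg at 30 minutes and above 1050 mg at 35 minutes. Carry the same wording into the MOP and the pharmacy and nursing instructions. Which limit should give way, if either, is a clinical decision for the sponsor.

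The cost is about one sentence in each of the two sections and a matching change to the MOP. No change to data collection, sample size or the PK analysis is needed.

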7.3 Modification of Study Intervention/Investigational Product for a Participant

No dosing adjustments are required for hepatic or renal impairment.

7.4 Accountability Procedures for the Study Intervention/Study Drugs

Each site will provide drug for their study participants. The drug accountability records will be maintained according to sites' pharmacy policies and procedures for clindamycin phosphate (IV), clindamycin hydrochloride (PO capsules) and clindamycin palmitate (PO oral solution). See MOP for specific details related to investigational product accountability.

7.5 Assessment of Participant Compliance with Study Intervention

Compliance with dosing will be determined using the participant's medication administration record and other applicable site supporting documentation. For those participants who are discharged on oral clindamycin and have not completed the PO PK visit, the participant or parent/guardian will keep a drug administration diary and all drugs will be accounted for at the outpatient PK study visit. Outpatient study visits should be scheduled around the participant's oral dosing schedule to ensure that pre-dose samples are drawn at the study visit.

7.6 Concomitant Medications of Interest/Treatments

Concomitant medications of interest are listed in **Appendix II**. Children who are prescribed one of these medications after receipt of study drug may continue in the study.

REDACTED

8 ASSESSMENT OF SAFETY

8.1 Specification of Safety Parameters

AEs will be collected during and after study drug administration and for 3 days following end of therapy with clindamycin. Results will be tabulated by MedDRA System Organ Class and Preferred Term.

8.2 Methods and Timing for Assessing, Recording, and Analyzing Safety Parameters

AEs will be collected from the time of consent, throughout the period of study drug administration, and for 3 days following end of therapy with clindamycin. See **Section 8.6** for clarification for AEs identified at the 3-day follow-up visit and for serious AEs (SAEs). Safety will be assessed by frequency and incidence of AEs and SAEs. The Best Pharmaceuticals for Children Act (BPCA) safety monitoring committee (DMC) convened by NICHD will review data and safety information from study participants.

8.2.1 Adverse Event

An **adverse event** (AE) is any untoward medical occurrence in humans, whether or not considered drug-related, which occurs during the conduct of a clinical trial. Any change in clinical status, ECGs, routine labs, x-rays, physical examinations, etc., that is considered clinically significant by the study investigator is considered an AE.

A **suspected adverse reaction** is any adverse event for which there is a reasonable possibility that the drug caused the adverse event. A reasonable possibility implies that there is evidence that the drug caused the event.

An **adverse reaction** is any adverse event caused by the drug.

A **serious adverse event** or **serious suspected adverse reaction** or **serious adverse reaction** as determined by the investigator or the sponsor is any event that results in any of the following outcomes:

1. Death
2. Life-threatening AE ("life-threatening" means that the study participant was, in the opinion of the investigator or sponsor, at immediate risk of death from the reaction as it occurred and required immediate intervention)
3. Persistent or significant incapacity or substantial disruption of the ability to conduct normal life functions
4. Inpatient hospitalization or prolongation of existing hospitalization
5. Congenital abnormality or birth defect

6. Important medical event that may not result in one of the above outcomes, but may jeopardize the health of the study participant or require medical or surgical intervention to prevent one of the outcomes listed in the above definition of serious event

8.2.2 Unexpected Adverse Event

This is defined as any adverse event, the specificity or severity of which is not consistent with the package insert, investigational plan, or informed consent.

8.2.3 Identification of Events and Timeframe for Reporting

As all participants in this study will have pre-existing medical conditions and may be currently hospitalized, those pre-existing conditions will not be considered as adverse events. New events that occur or pre-existing conditions that worsen in terms of frequency or intensity will be reported as adverse events.

All reportable events as defined above, determined to be an AE based on physical examination, laboratory findings, or other means, will be recorded in the source documents and entered in the CRF. Each event will be recorded on an AE CRF starting after consent has been obtained. The investigator will provide the date of onset and resolution, intensity, action(s) taken, changes in study drug dosing, relationship to study drug, and outcome. Any event beginning more than 3 days after the last dose of study drug will not be captured.

8.2.4 Follow-up of Adverse Events

AEs ongoing at the time of the last dose of study drug will be followed up to 3 days after the last dose of study drug. AEs that resolve during the study or follow-up period will have the resolution date documented in the CRF. Adverse events that are identified at the last assessment visit/phone contact (or at the early termination visit) must be recorded on the AE CRF, with the status of the AE noted. Any events that are identified at the last assessment visit/phone contact will be followed for an additional 3 days for AEs and 10 days for SAEs and if still ongoing can be "resolved by convention". All serious suspected adverse reactions will be followed until resolution. All enrolled participants in both cohorts who receive at least 1 dose of clindamycin will be followed for safety.

8.3 Guidelines for Assessing Intensity of an Adverse Event

The investigator should use the following definitions when assessing intensity of an adverse event:

1. **MILD:** Participant is aware of symptoms or has minor findings but tolerates them well, and no or minimal intervention required
2. **MODERATE:** Participant experiences enough symptoms or findings to require intervention
3. **SEVERE:** Participant experiences symptoms or findings that require significant intervention

8.4 Guidelines for Determining Causality

The investigator will use the following question when assessing causality of an adverse event to study drug: Is there a reasonable possibility that the drug caused the event? An affirmative answer designates the event as a suspected adverse reaction. "Reasonable possibility" means that there is evidence to suggest a causal relationship between the drug and the adverse event.

8.5 Reporting Procedures and Timeframe for Reporting

All AEs will be entered into the data system within 72 business hours of identification. All serious events will be entered into the data system within 24 hours of identification. If there are technical difficulties encountered when entering the event into the electronic data capture (EDC) system, the SAE will be reported to the data coordinating center (DCC) by telephone or FAX communication. Investigators must submit safety reports as required by their local IRB, independent of the reporting requirements specified in the protocol.

8.5.1 Serious Adverse Events

Any serious adverse event entered in the EDC system will generate an automatic email notification to the DCC, IND sponsor, protocol chair, and funding sponsor (NICHHD). The BPCA DCC medical monitor will review all SAEs at the time that they are reported. Investigators must also submit safety reports locally as required by their IRB.

8.5.2 Regulatory Reporting

Any event that requires expedited reporting based on federal regulations will be forwarded to the IND sponsor. The sponsor or his representative will submit expedited safety reports (IND safety reports) to the FDA and other regulatory agencies as necessary, and will inform the DMC and investigators of such regulatory reports. Site investigators must submit IND safety reports as required by their IRB. Documentation of the submission to and receipt by the IRB should be retained for each IND safety report. The sponsor will submit a progress report of the investigation annually, which will include a summary showing the most frequent and most serious adverse events by body system.

8.6 Type and Duration of Follow-up of Participants after Adverse Events

Adverse events will be followed by the investigator or a clinician member of the study team in person if the participant is hospitalized for an AE or SAE. If the participant is not hospitalized, the investigator or a clinician may review the participant's medical record, contact the participant by phone, or contact the participant's primary care physician for follow-up. Participants withdrawn from the study due to an AE, whether serious or non-serious, must be followed by the investigator. Refer to **Section 8.2.4** for follow-up of AEs/SAEs. The medical monitor or study principal investigator must be notified if the AE may relate to overdose of study treatment.

8.7 Halting Rules

Participant safety data will be reviewed on an ongoing basis to monitor for halting criteria.

The study enrollment and dosing will be halted for a safety review by the BPCA DMC if serious adverse reactions occur in ≥ 2 participants.

Furthermore, the NICHHD, the IND sponsor, protocol chair, the DMC, and the investigators shall have the right to recommend termination of this study at their discretion. Possible reasons for termination of the study include, but are not limited to:

1. Adverse events
2. Unsatisfactory enrollment with respect to quantity or quality

The study may be placed on hold or terminated at a site(s) for the following reasons:

1. Inaccurate or incomplete data collection
2. Falsification of records
3. Failure to adhere to the protocol

